4.3 Inclusion Criteria

All patients must meet the following criteria in order to be included in this study.

- a. Male or female patients \geq 18 years of age
- b. A life expectancy of at least 12 weeks with a Karnofsky performance status of at least 70 (Appendix II)
- c. The target lesion(s) can be accurately measured in at least one dimension according to RECIST
- d. No prior radiotherapy to the brain
- e. Previous or concurrent systemic or targeted chemotherapy is allowed
- f. Patients must have an extra-cranial primary tumor diagnosis
- g. Patients will have no more than 3 distinct lesions within the brain. At least 1 lesion must be a minimum of 3cm in greatest dimension, no larger than 5cm which will be treatable by fractionated stereotactic radiosurgery
- h. The additional lesions will each be treated with single fraction stereotactic radiosurgery
- i. Patient may be on steroids or anti-epileptics
- j. Must be aware of the neoplastic nature of his/her disease and willingly provide written, informed consent after being informed of the procedure to be followed, the experimental nature of the therapy, alternatives, potential benefits, side-effects, risks and discomforts
- k. Patients do not need a histologically proven diagnosis of brain mets

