6.4 Objective criteria for defining response

6.4.1. Tumor Response on MRI (RECIST)

Measurable Disease Response: CTEP's RECIST guidelines will be followed. A quick reference to the RECIST guidelines can be downloaded at the following URL:

<http://ctep.info.nih.gov/Policies/WordDocs/RCSTF.PH2TEMPF.doc>. (Appendix II)

Patients enrolled in this study must have a measurable brain metastasis which is defined as lesions that can be accurately measured in at least one dimension: [longest diameter to be recorded] on the MRI scan.

The same method of assessment and the same technique should be used to characterize each identified & reported lesion at baseline & during follow-up.

Taking into account the measurement of the longest diameter only for those lesions with size response, response criteria are defined as:

1. Complete Response (CR): the disappearance of a target lesion. Any pathological lymph nodes (whether target or non-target) must have reduction in short axis to <10 mm.
2. Partial Response (PR): at least a 30% decrease in the sum of diameters of target lesions, taking as reference the baseline sum diameters.
3. Progressive Disease (PD): at least a 20% increase in the sum of diameters of target lesions, taking as a reference the smallest sum on study (this includes the baseline sum if that is the smallest on study). In addition to the relative increase of 20%, the sum must also demonstrate an absolute increase of at least 5 mm. (Note: the appearance of one or more new lesions is also considered progression).
4. Stable Disease (SD): neither sufficient shrinkage to qualify for partial response nor sufficient increase to qualify for progressive disease, taking as reference the smallest sum diameters while on study.²¹

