6.4.1.2 Definition of local control

In this study, patients will be recorded as having a lesion that is locally controlled if they have stable disease (SD), partial response (PR), or complete response (CR) in the target lesion; all of which are defined above. Patients will be recorded as having local failure if they have progressive disease (PD) within the target lesion. Patients that develop new lesions outside the target volume will be coded as having a regional intracranial failure. A distant failure will be defined as new brain metastases outside of the treatment volume.

6.4.1.3

HRQL studies (Fact-Brain) will be completed prior to treatment, and following treatment to coincide with follow-up exams and MRI scans. See appendix III for a full version of the Fact-Brain questionnaire.

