7.0 Statistical Considerations

7.1 Definitions

Primary Objective

To determine the maximum tolerated dose (MTD) and safety of fractionated SRS when treating brain metastases

- Primary Endpoint: Maximum Tolerated Dose: the maximum amount of Gy fractionated stereotactic radiosurgery (FSRS) delivered without significant toxicity

Secondary Objectives

To evaluate the local control associated with this therapy.

To evaluate regional intracranial failure associated with this therapy.

To evaluate the Health Related Quality of Life (HRQL) associated with this therapy.

Secondary Endpoints

- Local control: proportion of patients with Complete Response (CR), Partial Response (PR), or Stable Disease (SD) in the target lesion
- Regional intracranial failure: proportion of patients that develop new lesions outside the target volume
- Health Related Quality of Life (HRQL) measured by Functional Assessment of Cancer Therapy – General (FACT-Brain) assessment.

The following definitions will be useful in explaining the trial design.

7.1.1 *Toxicity*

In this section, *toxicity* is taken to mean unacceptable, dose-limiting toxicity, as defined in Section 5.2.4, as any adverse event that occurs between the first fraction of radiotherapy and 60 days after the last fraction of radiotherapy. The primary goal of the TITE-CRM design employed in this trial is to identify the radiation dose associated with toxicity in 1/6=16.7% of patients (the MTD); this is referred to as the *target rate*.

7.1.3 *Expected rates of toxicity*

Based on previous treatment experience, the *expected rates of toxicity* have been estimated (Table 7.1). These rates will be re-evaluated throughout the trial as treatment experience is accrued in accordance with the TITE-CRM algorithm.

Radiation Dose	Expected Probability of Acute Toxicity
24 Gy	0.08
27 Gy	0.11
30 Gy	0.14
33 Gy	0.17
36 Gy	0.20

Table 7.1. Expected probabilities of toxicity

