7.3.2 Analysis of Secondary Endpoints

2. The proportion patients experiencing local control at each dose will be calculated with 95% exact confidence intervals. The dose-response function, describing the probability of local control at each dose, will be estimated using logistic regression, along with likelihood ratio profile confidence intervals.
3. The probability of failure will be analyzed in a similar fashion to the probability of intracranial failure.
4. The analysis of HRQL data (Section 6.5.1.4) will be descriptive. The data will be summarized by question at each time point with the frequency and percentage of each quality level. For each patient, the trajectory of the score will be plotted against time.

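### Regional intracranial failure can be counted, but its analysis is not specified: the failure codes overlap, one event has no category, and the only available template is a raw proportion with no time point

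*Combined protocol and SAP*

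**What the plan says.** Regional intracranial failure is one of three secondary endpoints. Sections 2.0 and 7.1 define it identically: "Regional intracranial failure: proportion of patients that develop new lesions outside the target volume".

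Section 6.4.1.2 gives three coding rules:
- Local: "Patients will be recorded as having local failure if they have progressive disease (PD) within the target lesion".
- Regional: "Patients that develop new lesions outside the target volume will be coded as having a regional intracranial failure".
- Distant: "A distant failure will be defined as new brain metastases outside of the treatment volume".

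Section 6.4.1 adds a note to the definition of progression: "Note: the appearance of one or more new lesions is also considered progression".

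A patient may enter with more than one brain lesion. Section 4.3 says "Patients will have no more than 3 distinct lesions within the brain" and "The additional lesions will each be treated with single fraction stereotactic radiosurgery".

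On analysis, section 7.3.2 item 2 covers local control: a proportion at each dose with an exact 95% interval, plus logistic regression on dose. Item 3 follows: "The probability of failure will be analyzed in a similar fashion to the probability of intracranial failure". Neither item names a time point.

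**The concern.** Three things are unsettled. The regional and distant codes describe the same event in consecutive sentences. Growth of an additional treated lesion is neither progression in the target lesion (if that means the fractionated one) nor a new lesion. Item 3 directs the analyst to a method that the plan does not contain.

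The third has the most consequence. An analyst would probably borrow item 2 and report a simple proportion by dose. In this population, a proportion with no time point mixes the risk of new brain lesions with the length of time patients stay under MRI. The result for objective 2.3 would be hard to interpret or to compare with another series.

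**Working it through.** The plan states no expected rate, precision or power for this endpoint, so there is no figure to reproduce. The check compares the definitions and then works out what a proportion without a time point measures.

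**1. Events against codes**
- *Growth of the fractionated lesion:* local failure. Clear.
- *New brain metastasis away from all treated sites:* meets both the regional and the distant rule in 6.4.1.2. The term treatment volume is not defined. Distant failure is not an endpoint and has no analysis.
- *Growth of an additional lesion (up to two, since 3 − 1 = 2):* no category in 6.4.1.2 on the single-target reading. Section 4.3(c) allows more than one target lesion, section 6.4.1 sums diameters over target lesions, and Appendix I makes measurable lesions targets (up to five per organ) and counts clear progression of non-target lesions as PD. None of these is mapped to local or regional failure.

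**2. The analysis reference**
Item 3 refers failure to the analysis of intracranial failure. No section gives that analysis. Item 2 is the only nearby template.

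**3. How much scanning a patient receives**
Inputs: MRI every 8–12 weeks for 24 months (6.2.1); follow-up for 24 months or until death (6.2); life expectancy of at least 12 weeks at entry (4.3b); removal for disease progression (8.1.1); median survival of 16 and 30 weeks in the two groups of the fractionation series cited in the background. That series had tumours under 3 cm, so it is only a rough guide.

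Follow-up scans by week T at 12-week intervals = T/12, rounded down:
- T = 16: 16/12 = 1.3, so 1 scan
- T = 30: 30/12 = 2.5, so 2 scans
- T = 104 (24 months): 104/12 = 8.7, so 8 scans

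Section 7.4 makes a patient without DLT evaluable one month after the last fraction. The first follow-up MRI is at 8–12 weeks, so an evaluable patient may have no follow-up MRI at all.

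**4. Effect on a raw proportion (illustration)**
Assume each scan has probability p of showing a first new lesion. The chance of being counted as a failure after k scans is 1 − (1 − p)^k.

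| p (assumed) | k = 1 | k = 2 | k = 8 |
|---|---|---|---|
| 0.05 | 5% | 10% | 34% |
| 0.10 | 10% | 19% | 57% |
| 0.20 | 20% | 36% | 83% |

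For example, 1 − 0.9^8 = 1 − 0.430 = 0.570. The underlying risk is the same along each row; only the time under observation differs.

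**5. Splitting by dose**
With at most 25 evaluable patients, one patient moves the overall proportion by 1/25 = 4 points. With an assumed five per dose, one patient moves a dose-level proportion by 1/5 = 20 points. Exact (Clopper–Pearson) 95% intervals for an illustrative 20%: 5/25 gives 6.8% to 40.7%; 1/5 gives 0.5% to 71.6%. Under section 7.2.2, higher doses are also reached later. If the analysis is run before everyone has completed follow-up, dose and length of follow-up are therefore mixed.

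**The case against.** The strongest reply is that the endpoint is already workable. Sections 2.0 and 7.1 give a yes/no count per patient, and 6.4.1.2 repeats it as a coding instruction. A second label that is not an endpoint does not take a patient out of that count. This stands. A reader might infer that the endpoint cannot be computed, or that coders would move nearly all new lesions to the distant code and empty the regional one. The documents support neither: nothing makes the codes mutually exclusive, and target volume and treatment volume are never defined as different regions.

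A reader might also infer that growth of an additional treated lesion is never a failure. Appendix I can score it as target or non-target PD. Because such a lesion is not new, it was never part of this endpoint's numerator; the gap bears more on local failure.

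Item 3 does not literally refer to itself. It looks like a wording slip, with local control probably meant. Item 2 also includes a model across doses, and section 7.3 plans generalized linear models to combine dose levels, with a descriptive fallback. The wide by-dose intervals are thus not the only planned output. But modelling on dose supplies no time point and does not allow for unequal follow-up, so the main difficulty remains.

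Finally, cumulative incidence is a different quantity from a proportion and has costs of its own. That is true, and the endpoint wording must change with it.

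**Conclusion.** The point holds as an unspecified analysis with untidy coding, not as an endpoint that fails. The overlap of codes and the place of additional lesions need clarification. The substantive weakness is that the only available template gives a raw proportion with no time point, where follow-up can run from no post-treatment MRI to 24 months of scans. In the illustration, the same per-scan risk of 10% gives anything from 10% to 57%. That spread rests on the assumed per-scan risk, a constant 12-week interval, and survival figures from a cited series in smaller tumours; it shows the direction and possible scale, not a forecast.

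Pooling over doses assumes that the dose to the target has little effect on new lesions elsewhere, which the documents do not state. This is a secondary endpoint with no test or decision rule attached, and the determination of the MTD is unaffected.

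**What to change.** Replace section 7.3.2 item 3 with:

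> Regional intracranial failure (any new brain lesion outside the target volume) will be estimated pooled over dose levels as cumulative incidence at 6 and 12 months from the first fraction, with exact definitions as follows: death without a prior new lesion is a competing event, and patients alive without a new lesion are censored at their last MRI. Counts by dose will be listed descriptively.

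Then:
- Align the endpoint wording in sections 2.0 and 7.1, and state the denominator, including patients with no follow-up MRI.
- In 6.4.1.2, delete distant failure or restrict it to extracranial disease. State that the target lesion is the fractionated one. Give progression of additional treated lesions its own code and report it.
- Reconcile section 6.2 (follow-up for 24 months or until death) with removal for progression in 8.1.1, stating whether MRI data are still collected after removal. If they are not, say that censoring at the last MRI may be informative.

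The 6- and 12-month points match those used for local control in the institutional series in the background. The MRIs are already scheduled. The cost is a few sentences, a little more analysis, and no by-dose model for this endpoint. The estimate still reflects mortality, as a risk in the presence of death should, and with at most 25 patients it will be imprecise, especially at 12 months.

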7.0 Statistical Considerations

7.1 Definitions

Primary Objective

To determine the maximum tolerated dose (MTD) and safety of fractionated SRS when treating brain metastases

- Primary Endpoint: Maximum Tolerated Dose: the maximum amount of Gy fractionated stereotactic radiosurgery (FSRS) delivered without significant toxicity

Secondary Objectives

To evaluate the local control associated with this therapy.

To evaluate regional intracranial failure associated with this therapy.

To evaluate the Health Related Quality of Life (HRQL) associated with this therapy.

Secondary Endpoints

- Local control: proportion of patients with Complete Response (CR), Partial Response (PR), or Stable Disease (SD) in the target lesion
- Regional intracranial failure: proportion of patients that develop new lesions outside the target volume
- Health Related Quality of Life (HRQL) measured by Functional Assessment of Cancer Therapy – General (FACT-Brain) assessment.

The following definitions will be useful in explaining the trial design.

7.1.1 *Toxicity*

In this section, *toxicity* is taken to mean unacceptable, dose-limiting toxicity, as defined in Section 5.2.4, as any adverse event that occurs between the first fraction of radiotherapy and 60 days after the last fraction of radiotherapy. The primary goal of the TITE-CRM design employed in this trial is to identify the radiation dose associated with toxicity in 1/6=16.7% of patients (the MTD); this is referred to as the *target rate*.

7.1.3 *Expected rates of toxicity*

Based on previous treatment experience, the *expected rates of toxicity* have been estimated (Table 7.1). These rates will be re-evaluated throughout the trial as treatment experience is accrued in accordance with the TITE-CRM algorithm.

Radiation Dose	Expected Probability of Acute Toxicity
24 Gy	0.08
27 Gy	0.11
30 Gy	0.14
33 Gy	0.17
36 Gy	0.20

Table 7.1. Expected probabilities of toxicity

7.2 Escalation Rule

The trial will be monitored using a modification of the Continual Reassessment Method (24) called Time-to-Event CRM (25). The TITE-CRM method assumes a simple model for the time to occurrence of toxic response as a function of dose, and thereby allows information from all patients enrolled in the trial to be employed when allocating a new patient to a dose level. Subjects will be continuously recruited throughout the trial, without recruitment pauses between dose levels.

7.2.1 Initial dose

Dosing will begin at 24 Gy, which will cause toxicity in an estimated 8% of subjects.

7.2.2 Criterion for Dose Allocation

Doses will be allocated to patients according to the TITE-CRM algorithm:

- Whenever a patient is presented for enrollment, the probability of toxicity will be estimated for each radiation dose, based on the initial expectations of toxicity (Table 7.1) and the incidence of toxicity in patients already treated, weighted by the amount of time those patients have been followed. The dose that has estimated toxicity closest but less than or equal to the target rate will be selected.
- Dose escalation will be restricted to one level between adjacent patients. To be assigned to a dose greater than 24 Gy, at least one patient must have completed two months of observation post-treatment at the next lower dose without dose-limiting toxicity.
- There is no restriction on the number of levels that the dose may be decreased between patients.
- Under this allocation schema, the radiation dose will increase until toxicity is observed, and will then tend to vary around the dose associated with the target rate. In order to allocate doses, the protocol statistician must be notified promptly of all dose-limiting toxicities.

7.2.3 Dose-Toxicity Function

Given total dose d , a logistic dose-toxicity model with parameter α ,

$$P(DLT|d) = e^{3+\alpha d} / (1 + e^{3+\alpha d}),$$

Will be used, where $\alpha=1.0$ represents the initial assumptions about the toxicity of treatment, as displayed in the 'Design' column of Table 7.1. This model, which has been widely used in CRM trials (24,26-29), is an approximation to the true, unknown, dose-toxicity model. The first two patients will be assigned to Level 1. When subsequent patients present for

enrollment, the expected probability of toxicity at each dose will be calculated, based on the prior distribution of α (Gaussian, with mean of 1 and standard deviation of 0.3) and the available data, using a SAS computer routine written especially for this application. The patient will be assigned to the level with estimated probability of toxicity closest to but not exceeding the target rate, 0.167, allowing for the escalation restrictions in Section 7.2.2.

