7.2.5 Operating characteristics

The operating characteristics of the trial design were evaluated in a simulation experiment. 750 TITE-CRM trials were simulated assuming the toxicity probabilities in Table 7.1, but with true toxicity probabilities as specified in Table 7.2. In simulations of Scenerio1, the assumed probabilities of toxicity are correct, but in Scenerio 2, the true probability is higher than assumed, and in Scenerio3 there is a jump in toxicity over the target rate between 27 Gy and 30 Gy.

Radiation Dose	Expected Probability of DLT	True Probabilities of DLT		
		Scenario 1	Scenario 2	Scenario 3
24 Gy	0.08	0.08	0.10	0.10
27 Gy	0.11	0.11	0.15	0.15
30 Gy	0.14	0.14	0.20	0.35
33 Gy	0.17	0.17	0.25	0.55
36 Gy	0.20	0.20	0.30	0.75

Table 7.2. Conditions for Monte Carlo Assessment of Operating Characteristics

The operating characteristics are described in Figure 7.1. Metrics described are numbers of patients treated at each dose, number of observed toxicity per dose, selected MTD and number of observed toxicity per trial. Roughly equal numbers of patients are treated at each dose in the first scenario (where the trial assumptions match the true probabilities of toxicity), with decreasing numbers of patients treated at higher doses in the second and third scenarios. In the second and third scenarios, medians of 0 or 1 DLT per trial result from treatment at doses of 33 or 36 Gy. The chosen target dose tends to be somewhat conservative in all three scenarios. In the third scenario, in 56% of the trials result in either 24% or 28% of the patients on study experiencing DLT, due to the large jump

in toxicity across the true target dose, while, in the other scenarios, the proportions of patients on study experiencing DLT is less than or equal to the target rate of 1/6 in over 70% of the simulated trials. The proportions of treated patients experiencing DLT are similar to what would be expected from the 3+3 design, while the accuracy of the TITE-CRM design is actually slightly conservative compared to 3+3.

[figure not shown]

Figure 7.1 Operating characteristics of trial design. Bars from left to right in all frames indicate the first, second and third scenarios (Table 7.2). In the top frames, the tick marks indicate the medians, and the top and bottom of the bars the 97.5th and 2.5th percentiles, respectively. Asterisks in the bottom left frame indicate the true target doses for the three scenarios

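### The dose-toxicity formula in Section 7.2.3, read with d as total dose in Gy, gives a DLT probability of about 1 at every level instead of the 0.08 to 0.20 of Table 7.1; the coded doses it needs are not stated

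*Combined protocol and SAP*

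**What the plan says.** Section 7.2.3 of the combined protocol and SAP begins "Given total dose d , a logistic dose-toxicity model with parameter" α, and gives P(DLT|d) = exp(3 + αd) / (1 + exp(3 + αd)). It states that α = 1.0 "represents the initial assumptions about the toxicity of treatment, as displayed in the 'Design' column of Table 7.1". The prior on α is Gaussian with mean 1 and standard deviation 0.3.

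Table 7.1 (Section 7.1.3) has one probability column, headed "Expected Probability of Acute Toxicity", with 0.08, 0.11, 0.14, 0.17 and 0.20 against 24, 27, 30, 33 and 36 Gy. No column is headed 'Design'. Section 7.2.1 repeats 8% for 24 Gy. Sections 3.3 and 5.2.3 give 24 to 36 Gy as the total doses and report that the MTD was found to be 36 Gy.

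For allocation, Section 7.2.3 says that "the expected probability of toxicity at each dose will be calculated" from the prior and the data, and then: "The patient will be assigned to the level with estimated probability of toxicity closest to but not exceeding the target rate, 0.167", subject to the escalation limits. Section 7.2.2 states the same rule. On the simulations, Section 7.2.5 reports: "Roughly equal numbers of patients are treated at each dose in the first scenario", "with decreasing numbers of patients treated at higher doses in the second and third scenarios".

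**The concern.** The intercept is +3, the design value of α is positive and total dose is positive, so the linear predictor is a large positive number at every level. A model said to represent an 8% risk at the starting dose then gives near-certain toxicity there. The formula and the table contradict each other.

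This matters because the formula is the core of the allocation. The allocation rule, the model and the follow-up weights (Sections 7.2.2 to 7.2.4) together determine each patient's dose, through a SAS routine written for this trial. A reader who wants to reproduce an allocation, or audit the routine, has only this formula to check it against. Programmed literally, the formula would not produce a working dose-finding design.

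**Working it through.** **Inputs.** Model, intercept 3, α = 1 and prior N(1, 0.3): Section 7.2.3. Doses and expected probabilities: Table 7.1. Weights: Section 7.2.4. Target 0.167: Sections 7.1.1 and 7.2.3.

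**1. Attempt to reproduce Table 7.1 as written.** At α = 1, 1 − P = 1 / (1 + exp(3 + d)).
- 24 Gy: 1 / (1 + e²⁷) = 1.9 × 10⁻¹²
- 36 Gy: 1 / (1 + e³⁹) = 1.2 × 10⁻¹⁷

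P is 1.000 at every level, so the table is not reproduced. For d > 0, any α ≥ 0 gives P ≥ expit(3) = 0.953. The prior puts only Φ(−1/0.3) = 0.0004 below zero.

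**2. Other readings of d.** At α = 1:
- Gy per fraction gives P above 0.9999.
- Level number 1 to 5 gives 0.982 to 0.9997.
- Gy/10 gives 0.996 to 0.999.
- Reversing the sign of d gives values below 10⁻⁹ (total Gy), or 0.0067 falling to 0.0001 (Gy per fraction).
- Reversing the intercept gives about 1 (total Gy), 0.35 to 0.65 (Gy/10) or 0.119 to 0.182 (d/24).

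None matches 0.08 to 0.20.

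**3. Values of d that do match.** Setting 3 + dᵢ = logit(pᵢ) gives dᵢ = logit(pᵢ) − 3:

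| Total dose | pᵢ | logit(pᵢ) | dᵢ |
|---|---|---|---|
| 24 Gy | 0.08 | −2.442 | −5.442 |
| 27 Gy | 0.11 | −2.091 | −5.091 |
| 30 Gy | 0.14 | −1.815 | −4.815 |
| 33 Gy | 0.17 | −1.586 | −4.586 |
| 36 Gy | 0.20 | −1.386 | −4.386 |

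Put back into the formula, these return Table 7.1 exactly. With intercept 3 and α = 1 they are unique.

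**4. What the literal model does with data.** The posterior of α was found by numerical integration. Each DLT-free patient contributes 1 − wP, the usual TITE-CRM form; Section 7.2.4 gives the weights w but not this expression, so it is an assumption.
- *No DLT in 2 patients at 24 Gy, both fully followed (w = 1).* The likelihood (1 − P)² is about 3.5 × 10⁻²⁴ at α = 1, so the posterior is driven below zero, to a mean of −0.193. P at that mean is 0.165, 0.100, 0.058, 0.034, 0.019 for 24 to 36 Gy. The posterior mean of P is 0.276, 0.221, 0.179, 0.146, 0.120. The values depend on the summary used, but under both the estimated toxicity falls as dose rises.
- *The same two patients half followed (w = 0.5).* The likelihood (1 − 0.5P)² is nearly flat at 0.25 where the prior has its mass. The posterior mean of α is 0.9996 and every level is estimated at about 1.

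**5. Which coding the simulations resemble.** Trials of 25 patients were simulated under Table 7.2 with the Section 7.2.2 limits. Three settings are assumptions, not in the documents: entry every 2, 4 or 10 weeks; DLT times uniform over 10 weeks; and 24 Gy kept as a computing placeholder, not a proposed rule, when no level qualified. In Scenario 1, raw Gy put a mean of 15 to 21 patients at 24 Gy and at most 0.6 at 36 Gy. Coded doses gave 5.5 to 9.3 and 1.7 to 8.9. Numbers largely fall with dose in Scenarios 2 and 3 under both codings, so only Scenario 1 separates them.

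**6. Two documentation gaps (coded doses, full follow-up).**
- *Posterior summary.* With 1 DLT in 4 patients at 24 Gy, the estimate at 24 Gy is 0.145 (P at the posterior mean of α), 0.170 (P at the mode) or 0.188 (mean of P). Against 0.167, only the first lets 24 Gy qualify.
- *No qualifying level.* With 1 DLT in the first 2 patients, the same three estimates are 0.224, 0.249 and 0.275. No level qualifies, and the text does not say what follows.

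**The case against.** The strongest reply is that this is a labelling slip which the documents themselves resolve. Section 7.2.3 ties α = 1 to Table 7.1, Section 7.2.2 bases estimation on that table, and Section 7.2.5 simulates from it. A statistician familiar with the CRM would infer coded doses, and they follow uniquely. Table 7.1 has only one probability column, so the 'Design' reference misleads nobody for long. The behaviour in step 4 describes a program that probably was never run. All of this stands, and it limits the weight of the point. It does not remove it: the text says total dose, states no coding, and cannot serve as the reference for checking a purpose-written routine.

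A reader might go further and infer that patients were allocated wrongly, or that the MTD of 36 Gy is unsound. The documents do not support that. Similar numbers per dose in Scenario 1 are hard to obtain with raw Gy. A reported MTD at the top level is also hard to square with a model that rarely reaches it. Neither is proof. The simulation comparison rests on assumed accrual, and even with coded doses equal numbers do not appear at every rate: with entry every 2 weeks the Scenario 1 medians were 5/5/5/5/1.

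It is also tempting to call the two gaps in step 6 errors. They are missing detail. The phrase "the expected probability of toxicity at each dose will be calculated" most naturally means the posterior mean of P, and nothing shows that the no-dose case arose.

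**Conclusion.** The written model is wrong, and this should be corrected. At α = 1 it gives P of about 1 at all five levels against a stated 0.08 to 0.20. That result is exact and needs no assumption beyond reading total dose in Gy, as the protocol does throughout. Run literally, the model fails as a dose-finding tool; that part rests on the stated prior and the usual TITE-CRM likelihood. The error is fully recoverable from Table 7.1 and the intercept. It is a fault in the specification, and it is not evidence against the allocations or the reported MTD. Whether the routine used the codes can be settled only by looking at the code.

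**What to change.** - In Section 7.2.3, replace total dose by a coded dose dᵢ = logit(pᵢ) − 3, and list −5.442, −5.091, −4.815, −4.586 and −4.386 for 24, 27, 30, 33 and 36 Gy.
- Replace the 'Design' column reference with the actual column of Table 7.1.
- Check once that the SAS routine and the Section 7.2.5 simulations used these values. Re-derive the allocations and any model-based MTD only if they did not.
- As minor documentation, state which posterior summary served as the expected probability, and record what was done, in the trial and in the simulations, if no level was at or below 0.167. The content of that rule is for the study team.

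The cost is a few lines of text and one code check. No extra patients are needed.
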